#### **8.14 Pregnancy Tests**

Serum pregnancy tests will be performed on women of childbearing potential during screening. Urine or serum pregnancy tests will be performed on women on Day 1 of each cycle prior to dosing. A negative pregnancy test result must be obtained before the administration of the study drug.

A pregnancy test does not need to be performed on women who are postmenopausal for at least 1 year or surgically sterile for at least 3 months before signing the ICF.

If a female subject becomes pregnant, administration of the study drug must be discontinued immediately.

## 9.0 ASSESSMENT OF EFFICACY EVALUATIONS

Documented tumor measurements are required using CT scans or MRI, as appropriate and are to be performed every 8 weeks ( $\pm$  7 days) and in line with standard of care. The same method of assessment (CT or MRI) and the same technique for acquisition of data must be used to characterize each identified and reported lesion at baseline, during the treatment period, and at the EOT visit (if previous assessment was not completed within 4 weeks).

Radiological imaging must include the pelvis, abdomen, and chest.

All subjects must have tumor measurements performed at the participating study center.

Efficacy analyses will be on data provided by the investigator site as well as an independent central imaging core laboratory. Site training, data collection, and analysis of all scans acquired during the study as per schedule of assessments will be detailed in a study manual and imaging charter.

Response and progression will be determined using the RECIST guidelines (version 1.1) ([Eisenhauer, 2009](#))

### 9.1 Definitions

At baseline, tumor lesions/lymph nodes will be categorized as measurable or non-measurable as described below.

#### 9.1.1 Measurable Disease

Target tumor lesions: Must be accurately measured in at least one dimension (longest diameter in the plane of measurement is to be recorded) with a minimum size of:

- 10 mm by CT scan (CT scan slice thickness no greater than 5 mm); when CT scans have slice thickness greater than 5 mm, the minimum size for a measurable lesion should be twice the slice thickness.

Malignant lymph nodes: To be considered pathologically enlarged and measurable, a lymph node must be  $\geq$  15 mm in short axis when assessed by CT scan (CT scan slice thickness recommended to be no greater than 5 mm). At baseline and in follow-up, only the short axis will be measured and followed.

### 9.1.2 Non-measurable Disease

All other lesions, including small lesions (longest diameter < 10 mm or pathological lymph nodes  $\geq 10$  to < 15 mm short axis) as well as truly non-measurable lesions, are considered non-measurable disease. Lesions considered truly non-measurable include: leptomeningeal disease, ascites, pleural or pericardial effusion, lymphangitic involvement of skin or lung, abdominal masses/abdominal organomegaly identified by physical exam that is not measurable by reproducible imaging techniques.

### 9.2 Specifications by Methods of Measurements

The same method of assessment and the same technique should be used to characterize each lesion at baseline and during follow-up. Imaging-based evaluation should always be done rather than clinical examination unless the lesion(s) being followed cannot be imaged but are assessable by clinical exam.

Clinical lesions: Clinical lesions will only be considered measurable when they are superficial and  $\geq 10$  mm diameter as assessed using calipers (e.g., skin nodules). When lesions can be evaluated by both clinical exam and imaging, imaging evaluation should be undertaken since it is more objective and may also be reviewed at the end of the study. For cutaneous lesions that are included in target lesions, digital photographs should be obtained and utilized for measurement.

CT, MRI: CT is the best currently available and reproducible method to measure lesions selected for response assessment. If a slice thickness > 5 mm is used for CT scanning, then the minimum longest diameter for a target lesion should be twice the slice thickness. MRI is also acceptable in certain situations (e.g., for body scans).

Tumor markers: Tumor markers alone cannot be used to assess objective tumor response. If markers are initially above the ULN, however, they must normalize for a subject to be considered in complete response.

Cytology, histology: These techniques can be used to differentiate between PR and CR in rare cases when the nature of a residual lesion is in question. The cytological confirmation of the neoplastic origin of any effusion that appears or worsens during treatment can be considered if the measurable tumor has met criteria for response or SD in order to differentiate between response (or SD) and PD.

## 9.2.1 Tumor Response Evaluation

### 9.2.1.1 Assessment of Overall Tumor Burden at Baseline and Measurable Disease

To assess objective response or future progression, it is necessary to estimate the overall tumor burden at baseline and use this as a comparator for subsequent measurements. Measurable disease is defined by the presence of at least one measurable lesion.

### 9.2.1.2 Baseline Documentation of ‘Target’ and ‘Non-target’ Lesions

When more than one measurable lesion is present at baseline all lesions up to a maximum of 5 lesions total (and a maximum of 2 lesions per organ) representative of all involved organs should be identified as target lesions and will be recorded and measured at baseline (this means in instances where subjects have only one or two organ sites involved a maximum of 2 and 4 lesions, respectively, will be recorded). Target lesions should be selected on the basis of their size (lesions with the longest diameter), be representative of all involved organs, but in addition should be those that lend themselves to reproducible repeated measurements. It may be the case that, on occasion, the largest lesion does not lend itself to reproducible measurement in which circumstance the next largest lesion which can be measured reproducibly should be selected.

Pathological nodes which are defined as measurable and may be identified as target lesions must meet the criterion of a short axis of  $\geq 15$  mm by CT scan. Only the short axis of these nodes will contribute to the baseline sum. All other pathological nodes (those with short axis  $\geq 10$  mm but  $< 15$  mm) should be considered non-target lesions. Nodes that have a short axis  $< 10$  mm are considered non-pathological and should not be recorded or followed.

A sum of the diameters (longest for non-nodal lesions, short axis for nodal lesions) for all target lesions will be calculated and reported as the baseline sum diameters. If lymph nodes are to be included in the sum, then as noted above, only the short axis is added into the sum. The baseline sum diameters will be used as reference to further characterize any objective tumor regression in the measurable dimension of the disease.

All other lesions (or sites of disease) including pathological lymph nodes should be identified as non-target lesions and should also be recorded at baseline. Measurements are not required and these lesions should be followed as ‘present’, ‘absent’, or in rare cases ‘unequivocal progression’.

### 9.2.1.3 Special Notes on the Assessment of Target Lesions

Lymph nodes: Lymph nodes identified as target lesions should always have the actual short axis measurement recorded (measured in the same anatomical plane as the baseline examination),

even if the nodes regress to below 10 mm on study. This means that when lymph nodes are included as target lesions, the ‘sum’ of lesions may not be zero even if complete response criteria are met, since a normal lymph node is defined as having a short axis of < 10 mm. For PR, SD and PD, the actual short axis measurement of the nodes is to be included in the sum of target lesions.

Target lesions that become ‘too small to measure’: While on study, all lesions (nodal and non-nodal) recorded at baseline should have their actual measurements recorded at each subsequent evaluation, even when very small (e.g., 2 mm). However, if the lesion is believed to be present and is faintly seen but too small to measure with any accuracy, a default value of 5 mm should be assigned.

## 9.2.2 Response Criteria using RECIST v1.1

### 9.2.2.1 Evaluation of Target Lesions

This section provides the definitions of the criteria used to determine objective tumor response for target lesions.

Complete Response (CR)	Disappearance of all target lesions. Any pathological lymph nodes (whether target or non-target) must have reduction in short axis to < 10 mm.
Partial Response (PR)	At least a 30% decrease in the sum of the longest diameters (SLD) of target lesions, taking as reference the baseline SLD
Progressive Disease (PD)	At least a 20% increase in the SLD of target lesions, taking as reference the smallest SLD on study (this includes the baseline sum if that is the smallest on study). In addition to the relative increase of 20%, the sum must also demonstrate an absolute increase of at least 5 mm. (Note: the appearance of one or more new lesions is considered progression.)
Stable Disease (SD)	Neither sufficient shrinkage to qualify for PR nor sufficient increase to qualify for PD, taking as reference the smallest sum diameters while on study.

### 9.2.2.2 Evaluation of Non-target Lesions

This section provides the definitions of the criteria used to determine the tumor response for the group of non-target lesions. While some non-target lesions may actually be measurable, they need not be measured and instead should be assessed only qualitatively at the time points of radiographic assessments.

Complete Response (CR)	Disappearance of all non-target lesions and normalization of tumor marker level. All lymph nodes must be non-pathological in size (< 10 mm short axis).
Non-CR/Non-PD	Persistence of one or more non-target lesion(s) and/or maintenance of tumor marker level above the normal limits.
Progressive Disease (PD)	Unequivocal progression of existing non-target lesions. (Note: the appearance of one or more new lesions is also considered progression).

**NOTE:** If tumor markers are assessed for a given subject and are initially above the ULN, they must normalize for a subject to be considered in complete CR.

### 9.2.2.3 Confirmatory Measurement/Duration of Response

#### 9.2.2.3.1 Confirmation

Confirmation of response (either PR or CR) is required. Changes in tumor measurements must be confirmed by repeat assessments that should be performed  $\geq 4$  weeks after the criteria for response are first met.

#### 9.2.2.3.2 Duration of Overall Response

DOR is measured from the time that measurement criteria are met for CR or PR (whichever is first recorded) until a documented PD per RECIST 1.1 or death.

#### 9.2.2.4 Evaluation of Overall Response using RECIST v1.1

**Table 6: Best Overall Response When Confirmation of CR and PR Required**

Overall Response First Time Point	Overall Response Subsequent Time Point	BEST Overall Response
CR	CR	CR
CR	PR	SD, PD, or PR a
CR	SD	SD provided minimum criteria for SD duration met, otherwise. PD
CR	PD	SD provided minimum criteria for SD duration met, otherwise. PD
CR	NE	SD provided minimum criteria for SD duration met, otherwise. NE
PR	CR	PR
PR	PR	PR
PR	SD	SD
PR	PD	SD provided minimum criteria for SD duration met, otherwise. PD
PR	NE	SD provided minimum criteria for SD duration met, otherwise. NE
NE	NE	NE

CR, complete response; PR, partial response; SD, stable disease; PD, progressive disease; NE, not evaluable

- a. If a CR is truly met at first time point, then any disease seen at a subsequent time point, even disease meeting PR criteria relative to baseline, makes the disease PD at that point (since disease must have reappeared after CR). Best response would depend on whether minimum duration for SD was met. However, sometimes ‘CR’ may be claimed when subsequent scans suggest small lesions were likely still present and in fact the subject had PR, not CR at the first time point. Under these circumstances, the original CR should be changed to PR and the best response is PR.

Source: [Eisenhauer, 2009](#)

## 10.0 STATISTICAL METHODS PLANNED IN THE PROTOCOL AND DETERMINATION OF SAMPLE SIZE

### 10.1 General Considerations

All analyses will be descriptive in nature and subject data will be listed. Descriptive statistics will be presented by dose level and for all subjects, and further summarized by tumor type.

All subjects that received at least 1 dose (or partial dose) of NKTR-214 will be considered evaluable for safety analysis. Safety will be assessed by the tabulation of AEs and review of laboratory evaluations. AEs, hematological and biochemical toxicity will be classified according to MedDRA 18.1 or later. All demographics, laboratory values, and vital signs will be summarized using descriptive statistics.

### 10.2 Determination of Sample Size

This is a Phase 1/2 dose escalation and dose expansion study. Cohorts of at least 3 subjects will be treated at each dose level during dose escalation and additional subjects will be added to each dose cohort based on the dose assignment action (escalate to a higher dose, stay at the same dose, or de-escalate to a lower dose) listed in [Table 4](#) or Sponsor determination of the need for additional data to further evaluate the benefit/risk profile. It is estimated that approximately 50 subjects will be enrolled into the dose escalation phase.

Dose Expansion will enroll approximately 50 subjects with RCC. Ongoing safety monitoring will be performed as detailed in Section [10.2.1](#).

#### 10.2.1 Expansion Cohorts Safety Monitoring

Bayesian sequential monitoring will be employed to perform ongoing safety monitoring targeting a toxicity rate of not more than 30% (where toxicity follows the same definition as a DLT defined in Section [4.1.2.1](#)) for the first 80 subjects enrolled in the dose expansion phase. Subjects will be monitored across tumor-specific cohorts after a minimum of 6 subjects treated at the selected dose for the dose expansion phase. The criteria for suspending enrollment due to safety are included in [Table 7](#) based on Bayesian sequential monitoring designs by [Thall et al. \(1995\)](#). The determination of the criteria is when:

$$\Pr [\text{prob}(\text{toxicity}) > 0.30 \mid \text{data}] > 0.95.$$

If there is a greater than 95% chance that the toxicity rate is greater than 30%, then accrual will be suspended and the safety review committee will meet to review safety data including aggregated safety summaries. We assume a beta (0.6, 1.4) prior distribution for the toxicity rate,

which has a mean of 0.3 corresponding to the 30% target toxicity rate. A constant 30% rate was chosen for the standard treatment rate.

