**1.0 STUDY SYNOPSIS**

Name of Sponsor:	Nektar Therapeutics
Name of Finished Product:	NKTR-214 drug product
Name of Active Ingredient:	NKTR-214 drug substance
Title of Study:	A Phase 1/2, Open-label, Multicenter, Dose Escalation and Dose Expansion Study of NKTR-214 in Subjects with Locally Advanced or Metastatic Solid Tumor Malignancies
Duration of Treatment:	Subjects will be treated until unacceptable toxicity, or disease progression per Response Evaluation Criteria in Solid Tumors (RECIST) version 1.1 (treatment may continue if there is clinical benefit as determined by the Investigator).
Phase of Development:	Phase 1/2
Objectives:	
The primary objectives are:
 
 
To evaluate the safety and tolerability, and define the maximum tolerated dose (MTD) of NKTR-214
 
To evaluate the efficacy of NKTR-214 by assessing the objective response rate (ORR) at the MTD or the dose below the MTD
 
 
The secondary objectives are:
 
 
To evaluate the efficacy of NKTR-214 by assessing best overall response (BOR), [REDACTED] duration of response (DOR), clinical benefit rate (CBR), time to response (TTR), [REDACTED]
 
To characterize the pharmacokinetic (PK) profile of NKTR-214 and relevant metabolites
 
To assess the immunogenicity of NKTR-214
 
 
The exploratory objectives are:
 
 
To assess the immunologic effect of NKTR-214 in tumor tissue on tumor-infiltrating lymphocytes (TIL)
 
To assess the immunologic effects of NKTR-214 in blood, including effects on cytokines, natural killer (NK) cells, T-cells, and other serum proteins and immune modulators
 

Study Population	Adults age 18 and older with histologically confirmed locally advanced or metastatic solid tumors in Part 1 (Dose Escalation) and renal cell carcinoma (RCC) in Part 2 (Dose Expansion) who have measurable disease
Number of Subjects (planned):	
Part 1: Approximately 50 subjects will be enrolled into the dose escalation phase of the study.
 
Part 2: Approximately 50 subjects will be enrolled into the dose expansion phase of the study.

Number of Study Sites:	Approximately 3 clinical study sites for dose escalation cohorts; up to 15 additional sites may be added for the dose expansion cohort.
Countries:	USA

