#### 4.1.2.2 Part 2: Dose Expansion Scheme

At least 1 study Investigator and the Sponsor Medical Monitor will meet and decide the dose to be studied in Part 2 before the initiation of the dose expansion cohort (either the MTD dose or dose lower than MTD). This dose will be the recommended Phase 2 dose (RP2D), and all subjects in the expansion cohort will receive this dose. The RP2D may also be determined based on a biological effect of the study drug as determined by anti-tumor activity and immune activation. The RP2D for dose expansion will be communicated via an administrative dosing letter and enrollment in the expansion phase may begin without a protocol amendment.

Approximately 50 subjects with renal cell carcinoma (RCC) will be enrolled into Part 2. Subjects in the expansion cohort will be treated until tumor progression (treatment may continue if there is clinical benefit), death, unacceptable toxicity, symptomatic deterioration, achievement of maximal response, subject choice, the Investigator's decision to discontinue treatment, the subject withdraws consent, or Nektar Therapeutics decides to terminate the trial.

Note: The sponsor reserves the right to evaluate two doses or two dosing schedules in each expansion cohort if necessary based on the safety profile during the dose escalation portion.

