**Table 7: Suspension Boundaries for Toxicity During Expansion**

Total Number of Treated Subjects	Suspending Accrual if $\geq$ Number of Subjects with Toxicity
1-5	Not Applicable
6-8	5
9-10	6
11-12	7
13-15	8
16-18	9
19-20	10
21-23	11
24-25	12
26-28	13
29-31	14
32-34	15
35-36	16
37-39	17
40-42	18
43-45	19
46-48	20
49-50	21
51-53	22
54-56	23
57-59	24
60-62	25
63-65	26
66-68	27
69-71	28
72-73	29
74-76	30
77-79	31
80	Maximum enrollment for safety monitoring

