**Table 8: Operating Characteristics for Subject Accrual Suspension Rules**

True Toxicity Rate	Accrual Suspension Probability	Achieved Sample Size		
		25th	50th	75th percentiles
0.1	0.001	80	80	80
0.2	0.018	80	80	80
0.3	0.202	80	80	80
0.4	0.759	14	34	80
0.5	0.991	7	14	25
0.6	1.000	6	8	14

An internal safety review committee consisting of representatives from Clinical Development, Drug Safety, Biostatistics, other functional representatives, as needed, and at least one Principal Investigator will meet at least quarterly to review safety data for potential safety risks or more frequently if needed. If it is determined there is a high probability of observing more than 30% toxicities, enrollment will be suspended and the safety review committee will be convened to make a recommendation on the continuation, modification, or discontinuation of the study.

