4 DETERMINATION OF SAMPLE SIZE

In the dose escalation phase, cohorts of at least 3 subjects will be treated at each dose level and additional subjects may be added to each dose cohort based on the dose assignment action (escalate to a higher dose, stay at the same dose, or de-escalate to a lower dose) or Sponsor determination of the need for additional data to further evaluate the benefit/risk profile. It is estimated that approximately 50 subjects will be enrolled during the dose escalation phase.

Dose expansion will enroll approximately 50 subjects with RCC.

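### Table 8 gives operating characteristics for 80 expansion subjects, but Part 2 enrols about 50: at a 40% toxicity rate the suspension probability is about 0.62, not 0.759

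*Protocol*

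**What the plan says.** Protocol Section 10.2.1 suspends accrual when the posterior probability that the toxicity rate exceeds 0.30 is above 0.95, under a beta(0.6, 1.4) prior. The rule operates "for the first 80 subjects enrolled in the dose expansion phase", and the section adds: "Subjects will be monitored across tumor-specific cohorts after a minimum of 6 subjects treated at the selected dose". Table 7 lists boundaries for 6 to 79 treated subjects; its last row, at 80, carries only the label "Maximum enrollment for safety monitoring". Table 8 ("Operating Characteristics for Subject Accrual Suspension Rules") gives a suspension probability and three percentiles of achieved sample size for true rates from 0.1 to 0.6. Ten of its eighteen percentile entries are 80.

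The planned size of Part 2 is different, and it is stated consistently:

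- Protocol synopsis: "Approximately 50 subjects will be enrolled into the dose expansion phase of the study".
- Protocol Section 4.1.2.2: "Approximately 50 subjects with renal cell carcinoma (RCC) will be enrolled into Part 2".
- Protocol Section 10.2: "Dose Expansion will enroll approximately 50 subjects with RCC". Its next sentence sends the reader to Section 10.2.1 for the safety monitoring.
- SAP Section 4: "Dose expansion will enroll approximately 50 subjects with RCC".

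Protocol Section 12.1 requires an amendment before the sample size rises above what is specified.

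**The concern.** The monitoring section describes a larger expansion, with several tumor types, than the one the protocol now plans. A boundary at a given number of subjects depends only on the data so far, so a longer Table 7 does no harm. Operating characteristics do depend on the maximum. Each probability in Table 8 includes suspensions between subjects 51 and 80, who are not planned.

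Table 8 is the only quantitative statement in either document of how well the rule detects an excessive toxicity rate. An ethics board, an investigator or the safety review committee would read it as a property of this trial. In the row just above the 30% target, it is more reassuring than the planned cohort justifies.

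**Working it through.** **Inputs (Protocol Section 10.2.1, Tables 7 and 8).** Beta(0.6, 1.4) prior; threshold rate 0.30; posterior cut-off 0.95; first look at 6 subjects; stated maximum 80. Planned size of about 50 from Protocol Section 10.2 and SAP Section 4. Assumption: a look after each subject.

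**Step 1: the boundaries.** After x toxicities in n subjects the posterior is Beta(0.6 + x, 1.4 + n − x). The boundary is the smallest x for which Pr(rate > 0.30) > 0.95.

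- n = 6: x = 4 gives 0.945 and x = 5 gives 0.991, so the boundary is 5.
- n = 50: x = 20 gives 0.926 and x = 21 gives 0.959, so the boundary is 21.

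Both agree with Table 7. Repeating this for every n from 6 to 79 gives no mismatch.

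**Step 2: the suspension probability.** Let f(n, x) be the probability of having x toxicities after n subjects without earlier suspension, and let p be the true rate. Then

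f(n, x) = (1 − p) · f(n − 1, x) + p · f(n − 1, x − 1).

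At each n from 6 on, the mass at or above the boundary is removed and counted as suspended. The suspension probability is the sum of the removed mass up to the maximum. This is exact; no simulation is involved.

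**Step 3: reproduce Table 8, then change only the maximum.**

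| True rate | Table 8 | Max 80 | Max 50, last look at 50 | Max 50, last look at 49 |
|---|---|---|---|---|
| 0.1 | 0.001 | 0.0005 | 0.0005 | 0.0005 |
| 0.2 | 0.018 | 0.0181 | 0.0179 | 0.0179 |
| 0.3 | 0.202 | 0.2019 | 0.1727 | 0.1711 |
| 0.4 | 0.759 | 0.7593 | 0.6222 | 0.6144 |
| 0.5 | 0.991 | 0.9905 | 0.9465 | 0.9423 |
| 0.6 | 1.000 | 1.0000 | 0.9985 | 0.9982 |

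At a maximum of 80 every probability agrees with Table 8 to within 0.001, so both the method and the 80-subject basis are confirmed. The last column is shown because Table 7 gives no boundary in its own final row, which leaves open whether the last subject counts as a look.

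At a rate of 0.4 the difference is 0.759 − 0.622 = 0.137. The chance of never suspending is 1 − 0.759 = 0.241 as stated, against 1 − 0.622 = 0.378 (or 1 − 0.614 = 0.386) for 50 subjects. At 0.5 it is about 1% as stated and about 5% for 50.

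**Step 4: sensitivity.**

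- *Enrolment is approximate.* For 45 to 55 subjects the value at 0.4 runs from 0.592 to 0.644 with a final look, and from 0.577 to 0.638 without one.
- *Fewer looks.* Looking every 2, 3 or 5 subjects gives 0.611, 0.588 or 0.575 at a maximum of 50. At a maximum of 80 those schedules give 0.745, 0.717 and 0.716, so they do not reproduce the stated 0.759, whereas a look after each subject does.

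**Step 5: achieved sample size.** For a maximum of 50 the 25th/50th/75th percentiles are 50/50/50 at rates 0.1, 0.2 and 0.3; 14/34/50 at 0.4; 8/14/25 at 0.5; and 7/8/14 at 0.6. They are the same under either last-look convention.

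Three stated percentiles differ slightly from the exact values even at a maximum of 80: the 75th at 0.4 is 78 (stated 80), the 25th at 0.5 is 8 (stated 7), and the 25th at 0.6 is 7 (stated 6). Simulation or another percentile convention could explain these; they are separate from the present point.

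**The case against.** The strongest reply is that Table 8 contains no miscalculated probability. The text, the last row of Table 7 and the sample-size columns all show a horizon of 80, so a careful reader can see what the figures are conditional on. That is correct, and the fault is best described as a mismatch between the monitoring horizon and the planned enrolment. It does not make the table usable: Section 10.2 states 50 and then points directly to it, and neither document gives figures for 50.

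A second reply is that nothing changes in conduct. This also stands. The boundaries hold through subject 50, crossing one only suspends accrual pending review, and the safety review committee meets at least quarterly in any case. The effect is also concentrated. Only the 0.4 row moves by a large amount, the median there stays at 34, and the fall at 0.3 means fewer suspensions when the true rate equals the target, which is favourable.

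Third, the replacement figures are themselves conditional on a single pooled cohort. Protocol Section 4.1.2.2 reserves the right to study two doses or schedules. If counts were kept separately, with 25 subjects each (an assumption), the value at 0.4 would be about 0.42 per group. This qualifies 0.622, but it moves the answer further from 0.759.

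**Conclusion.** The point holds. Table 8 describes an 80-subject expansion that the current protocol does not plan. For a single cohort of 50 with a look after each subject from the sixth, detection at a true toxicity rate of 0.4 is 0.622 (0.614 if the last look is at 49), and no size from 45 to 55 comes near 0.759. The rows at 0.3 and 0.5 are overstated by smaller amounts, the rows at 0.1 and 0.2 are unaffected, and the row at 0.6 barely moves. The consequence is a misstated sensitivity for the safety rule, not a wrong rule. It should be corrected, but it does not call the conduct of the monitoring into question.

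**What to change.** At the next protocol amendment:

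1. Reword Section 10.2.1 so that the monitoring horizon and the reference to several tumor-specific cohorts match one renal cell carcinoma cohort of about 50.
2. Recompute Table 8 for that maximum and say whether the final subject counts as a look. For rates 0.1 to 0.6 the probabilities are 0.001, 0.018, 0.173, 0.622, 0.947 and 0.999 with a look at 50, or 0.001, 0.018, 0.171, 0.614, 0.942 and 0.998 with the last look at 49. Replace the sample-size percentiles with those in Step 5, and state the percentile convention, since two of the small changes there (8 for 7 and 7 for 6) do not come from the change of maximum.
3. State that the figures assume one pooled dose and schedule, and how subjects would be counted if the two-dose or two-schedule option were used.
4. Leave the Table 7 boundaries as they are. Rows just above 50 may stay, because enrolment is approximate; the final row at 80 should be brought into line with the planned size.

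The cost is one recomputed table and a few sentences. No boundary changes and no subjects are added; the stated sensitivity becomes less favourable.

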## **6.9 Determination of Dose-Limiting Toxicities**

Based on the preclinical toxicology data and the anticipated half-life of NKTR-214 (15-20 hours), drug-related toxicity is most likely to occur during treatment or within 10 days following treatment. Based on this, dose-limiting toxicities (DLTs) will be assessed in the first cycle for all subjects enrolled to a specific cohort (same dose level). If DLTs are not observed, dose escalation will be permitted and enrollment will begin at the next successive ascending dose cohort. Intra-subject dose escalation will not be permitted. Dose reduction is allowed in subjects based on toxicity with approval from the Medical Monitor.

Unless otherwise suggested by clinical data, a dose-limiting toxicity (DLT) is defined as a Grade 3 or higher study drug-related or possibly related AE occurring within the first cycle of dosing (excluding Grade 3/4 transient lymphopenia < 14 days in duration, tumor flare defined as local pain, irritation, or rash localized at sites of known or suspected tumor, a transient, reversible  $\leq$  grade 3 infusion AE, non-clinically significant laboratory abnormalities, or fatigue lasting less than 72 hours) using NCI CTCAE version 4.03.

Delayed DLTs are drug-related adverse events that occur after Cycle 1. Delayed DLTs will not be used to determine the MTD for dose escalation. Delayed DLTs will be collected and evaluated by the Investigators and the Sponsor on an ongoing basis.

All drug related adverse events after Cycle 1 will continue to be collected and evaluated by the Investigators and the Sponsor on an ongoing basis and will be taken into consideration in determining the MTD.

All AEs that meet DLT criteria, as well as any  $\geq$  Grade 3 immune-related adverse event (regardless of attribution), must be reported to the Sponsor, within 24 hours using the same rapid notification procedures that are used for serious AEs (Section 8.7).

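### If the reserved second dose or schedule is opened in Part 2, the Table 7 toxicity rule has no by-arm trigger (minor, conditional)

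*Protocol*

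**What the plan says.** Protocol 4.1.2.2 sets one recommended Phase 2 dose and states that "all subjects in the expansion cohort will receive this dose". A note at the end of the same section adds: "The sponsor reserves the right to evaluate two doses or two dosing schedules in each expansion cohort if necessary based on the safety profile". The synopsis allows 21-, 14- or 28-day dosing in Part 2.

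Protocol 10.2.1 defines the safety rule. Accrual is suspended when the posterior probability that the toxicity rate exceeds 30% is above 95%, under a Beta(0.6, 1.4) prior. The rule runs "for the first 80 subjects enrolled in the dose expansion phase", and "Subjects will be monitored across tumor-specific cohorts after a minimum of 6 subjects treated at the selected dose for the dose expansion phase". Table 7 has one boundary column, indexed by "Total Number of Treated Subjects". Part 2 is planned at about 50 subjects with RCC.

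The text after Table 8 gives the internal safety review committee a more general power: "If it is determined there is a high probability of observing more than 30% toxicities, enrollment will be suspended". It meets at least quarterly. Under Protocol 6.9, events meeting the DLT criteria "must be reported to the Sponsor, within 24 hours using the same rapid notification procedures that are used for serious AEs".

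The SAP contains no suspension rule. SAP 5 presents expansion data by tumor type and overall. Protocol 10.1 plans descriptive statistics by dose level, and SAP 10.1 summarises DLTs by dose cohort.

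**The concern.** Section 10.2.1 is written for one dose. If two arms were opened, there are two ways to read it, and neither gives a clear rule for each arm.

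- Read as a total count, which is what the Table 7 column label and the 80-subject limit suggest, it tests the average toxicity rate over the arms. A well-tolerated arm can then hide a toxic one.
- Read as limited to the selected dose, it leaves a second dose with no clear rule, and it still pools two schedules of one dose.

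Table 7 is the only numerical trigger for suspending accrual in Part 2. What is at stake is how likely that trigger is to fire when one arm is well above 30% and the other well below.

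**Working it through.** **Inputs from the Protocol.** Prior Beta(0.6, 1.4), 30% limit, 95% threshold and a start at 6 subjects (10.2.1); boundaries (Table 7); about 50 subjects in Part 2 (10.2).

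**Assumptions, not in the documents.** The option is used; 25 subjects per arm; accrual alternates, toxic arm first in each pair; toxicity is known at once; true rates are illustrative.

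**Step 1: reproduce the plan's figures.** After x toxicities in n subjects the posterior is Beta(0.6 + x, 1.4 + n − x). The boundary b(n) is the smallest x with 1 − F(0.30) > 0.95, where F is the posterior distribution function.

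- n = 25: x = 12 gives 0.963 and x = 11 gives 0.918, so b = 12.
- n = 50: x = 21 gives 0.959 and x = 20 gives 0.926, so b = 21.

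All boundaries for n = 6 to 79 match Table 7. For the operating characteristics I used the exact recursion P_n(x) = P_{n−1}(x)(1 − p_n) + P_{n−1}(x − 1)p_n, removing the probability at x ≥ b(n) after each subject from n = 6. To n = 79 this gives 0.001, 0.018, 0.202, 0.759 and 0.990 at true rates of 10% to 50%. Table 8 has 0.001, 0.018, 0.202, 0.759 and 0.991. The rule is sound for one arm.

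**Step 2: two arms.** The pooled count uses the same recursion over 50 subjects, with p_n alternating between the arms. The toxic arm alone uses 25 subjects. The last column is the probability that either the toxic-arm or the pooled boundary is crossed.

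| True rates | Average | Pooled only | Toxic arm alone | Either |
|---|---|---|---|---|
| 40% / 20% | 30% | 0.164 | 0.418 | 0.444 |
| 50% / 20% | 35% | 0.356 | 0.764 | 0.777 |
| 40% / 30% | 35% | 0.373 | 0.418 | 0.521 |
| 50% / 40% | 45% | 0.832 | 0.764 | 0.890 |

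At 40%/20% the average is (25 × 0.40 + 25 × 0.20)/50 = 0.30, exactly the target. The pooled rule therefore behaves much as it does for two arms that are both acceptable at 30% (0.173).

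**Step 3: sensitivity at 40%/20%.**

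- Order: the pooled probability is 0.437 if the toxic arm enrols first and 0.069 if the mild arm does.
- Split, pooled v toxic arm alone: 0.078 v 0.290 with 15 toxic and 35 mild; 0.306 v 0.511 with 35 and 15.
- Delay before a DLT is known: the documents give no accrual rate, so I assume 0, 4, 8 or 12 further entries over both arms. Expected toxic-arm enrolment, pooled v alone, is 22.5 v 19.9, 22.8 v 20.7, 23.1 v 21.4 and 23.4 v 22.1. The saving falls from 2.6 to 1.3 subjects, or from 1.0 to 0.5 DLTs at a 40% rate. At 40%/30% there is no saving.

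**Step 4: could a toxic arm reach Part 2?** Under the MTD definition of at most 1 DLT in 6 (4.1.2.1), a dose passes with probability (1 − p)^6 + 6p(1 − p)^5. This is 0.233 at 40% and 0.109 at 50%, so the 40% rows are the more relevant.

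**Step 5: cost in false suspensions.** With both arms at 30%, any suspension has probability 0.173 pooled only, 1 − (1 − 0.12676)² = 0.237 per-arm only, and 0.282 with both checks. With both at 20% the figures are 0.018, 0.033 and 0.043.

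**The case against.** The strongest reply is that the gap depends on several conditions and that other safeguards cover much of it. The base plan is one dose, at or below the MTD. Harm needs the option to be used, one arm well above 30% after escalation, the other well below, and the toxic arm not enrolling first. The study is open-label, DLT-level events are reported within 24 hours, and the clause after Table 8 lets the committee suspend for a high probability of excess toxicity without tying that to the Table 7 total. It could apply that judgement to one arm. All of this stands and limits the weight of the point. It does not supply a stated threshold by arm.

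A reader might infer from SAP 5 that nobody would see Part 2 toxicity split by arm. The documents do not support that for two doses, given Protocol 10.1 and SAP 10.1. It remains open only for two schedules of one dose.

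A reader might also infer that a second arm can open with no amendment, because "enrollment in the expansion phase may begin without a protocol amendment". That sentence concerns starting expansion at the single recommended dose. Protocol 12.1 requires an amendment for doses or schedules the protocol does not already specify, while the two-arm option and the 14- and 28-day schedules are already named. Whether an amendment would be needed is unsettled, so it is only possible that no later step would prompt a revision of the rule.

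The benefit is also modest where it is most relevant: 2.6 subjects at most at 40%/20%, falling with reporting delay. Those enrolment figures are for the toxic arm counted alone; I have none for the combined rule.

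**Conclusion.** A minor, conditional gap. Table 7 and Table 8 contain no error that matters, and a reader should not take this as a flaw in the rule for one dose and one schedule. If two doses or two schedules are run, Table 7 as written is one total count with no by-arm trigger. Under the assumed 25 + 25 alternating design, the chance of suspension at 40%/20% is 0.164 instead of 0.418, and at 50%/20% it is 0.356 instead of 0.764. Counting the toxic arm alone adds little at 40%/30% (0.418 v 0.373) and is worse than pooling at 50%/40% (0.764 v 0.832), which is why the pooled count should be kept too. The sizes depend on the assumed split, order, rates and delay; the absence of a by-arm rule does not.

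**What to change.** Add to Protocol 10.2.1: *If two doses or two schedules are opened in Part 2, Table 7 is applied separately to each dose-schedule arm from its sixth treated subject, and a crossing suspends accrual to that arm; the pooled count is kept as an additional check.* State the per-arm operating characteristics for about 25 subjects: suspension probability 0.017, 0.127, 0.418 and 0.764 at true rates of 20%, 30%, 40% and 50%.

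The boundaries depend only on the number treated, so no new table and no extra subjects are needed. Because the pooled count stays, the chance of a crossing is never below that of the present rule. The text is needed only before a second arm opens. Making the single-dose sentence in 4.1.2.2 subject to the note below it is optional tidying.

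The cost is the extra false suspensions shown in step 5; each leads to committee review, not to automatic termination. The fix also has a limit: at 25 subjects the per-arm rule alone still misses a 40% arm 58% of the time (1 − 0.418).
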